### **1.3. Secondary Objectives**

For the primary and secondary objectives, patients will be followed up to 90 days.

- Compare demographics, Charlson comorbidity index, and social determinants of health among patients (hunger vital signs, home, education, employment, social and emotional health) between the two arms of the study
- Compare the patient-centric 90-day utilization rate after the index primary care visit
- Compare the 90-day primary care utilization rate after the index primary care visit
- Compare the pharmacy related 90-day total cost of care after the index primary care visit
- Stratify and report outcomes by index primary care visit diagnoses (substance use disorder, depression/dysthymia, anxiety)

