#### 5.1.2. Rates and Variable Descriptions

- a. Demographic characteristics (age, race, gender, insurance plan)
- b. Charlson comorbidity index score

If we determine that we can identify hospital and primary care visits through claims data, we will use that as a source over using just Atrium Health encounters for the utilization rates as specified below.

- c. Patient-centric defined 90-day utilization rate. This is a utilization rate among patients with an ED, inpatient, or observation encounter to any Atrium Health facility ( $\leq 90$  days after the primary care visit).
- d. The 90-day primary care utilization rate. This is a utilization rate among patients with a primary care encounter ( $\leq 90$  days after the primary care visit).
- e. Primary care visit
  - i. At least one CPT code for preventative or outpatient visit
- f. Pharmacy related 90-day total cost of care. The pharmacy total cost of care is defined as the summation of all pharmacy paid claims within 90 days of the primary care visit among patients with pharmacy claim data ( $\leq 90$  days after the primary care visit).

Symptom and health outcomes are assessed at 3, 6, 9, and 12-months among patients who enrolled in the VBHI program.

- g. Asses symptom improvement for depression
  - i. Pre- PHQ-9 score from primary care visit
  - ii. Post- PHQ-9 score
- h. Primary care visit diagnoses (primary or secondary billed diagnoses)
  - i. substance use disorder
  - ii. depression/dysthymia
  - iii. anxiety
- i. Anxiety
  - i. Pre- GAD-7 score from initial enrollment
  - ii. Post- GAD-7 score

- j. Suicidal ideation
  - i. Pre- PHQ-9, Q9 score from primary care visit
  - ii. Post- PHQ-9, Q9 score
- k. Remission of depressive symptoms
  - i. PHQ-9 less than 5 in 2 consecutive months
- l. BMI
  - i. Pre- BMI level from primary care visit
  - ii. Post- BMI level
- m. HbA1c among diabetic patients
  - i. Pre- A1c level from primary care visit
  - ii. Post- A1c level
- n. LDL cholesterol level
  - i. Pre- LDL level from primary care visit
  - ii. Post- LDL level
- o. Hunger vital signs – reported upon enrollment
  - i. Within the past 12 months, we worried whether our food would run out before we got the money to buy more?
  - ii. Within the past 12 months the food we bought just didn't last and we didn't have the money to get more?
- p. Home – reported upon enrollment
  - i. What is your housing situation today?
  - ii. Are you worried about losing your house?

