## **6.2. Statistical analysis**

Prior to analysis, descriptive statistics will be calculated to screen all variables for accuracy and to examine distributions.

All analyses will follow the intention-to-treat (“ITT”) principle, such that patients will be analyzed based on the assignment of their primary care site to the VBHI program or usual care. Balance in baseline characteristics between the groups will be assessed using Student’s t-test for normally distributed data, the Wilcoxon rank sum test for ordinal data or interval data that are not normally distributed, and the chi-square test for categorical data. Normality will be assessed using the Shapiro Wilk test and Q-Q plots.

The primary outcome, total cost of care, will be compared between the VBHI and usual care groups using a linear mixed-effects model with a random effect to account for within-practice correlation. The primary predictor in the model is an indicator for assignment to the VBHI program versus usual care. Additional baseline covariates will be included in the model if they are either strongly correlated with the dependent variable or show baseline imbalance between the two groups.

The secondary outcome of pharmacy-related total cost of care will be compared between treatment groups using the same approach as for the primary outcome. A similar approach will be used to compare 90-day patient-centric, primary care, and avoidable care utilization rates, except the models will be generalized linear mixed models with a logit link, where utilization (yes/no) is the binary dependent variable.

Sub-analyses of the primary and secondary outcomes using the above methods will be performed on the data stratified by index primary care visit diagnosis.

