In addition, per-protocol analyses of the primary and secondary outcomes will be performed to evaluate the effect of VBHI program participation, in contrast to the ITT analysis evaluating the effectiveness of referral to the program. The per-protocol analyses will include only subjects who received and adhered to the treatment (VBHI program or usual care) assigned to their clinic. The analyses will be similar to those described above for ITT, except the primary predictor is an indicator for treatment (VBHI program or usual care) received rather than treatment assigned. To help address confounding due to incomplete adherence, the per-protocol analyses will adjust for pre-randomization and post-randomization factors that predict adherence. To identify such factors, a separate, multivariable logistic regression analysis will be performed on the full dataset with adherence (yes/no) as the dependent variable.

Exploratory analyses will evaluate baseline to 3-, 6-, 9-, and 12-month changes in symptom improvement and health outcomes using generalized linear mixed models with a logit link, where the dependent variable is binary (e.g., 50% reduction of PHQ-9 score from initial assessment (yes/no)). Random effect terms in the model will account for within-practice clustering and within-patient correlation. Fixed effects will be the treatment group indicator, time indicator, and interaction between treatment group and time.

All tests will be two-sided and the data will be analyzed using SAS Enterprise Guide 7.1 (SAS Institute Inc., Cary, NC, USA).

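### The diagnosis sub-analyses refit the arm comparison in strata that can overlap, with no arm-by-diagnosis interaction, so they cannot show whether the effect differs by diagnosis

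*Combined protocol and SAP*

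**What the plan says.** Section 6.2 sets out mixed models for total cost and for the secondary outcomes. On the treatment term for total cost it says: "The primary predictor in the model is an indicator for assignment to the VBHI program versus usual care". Pharmacy cost follows suit: "The secondary outcome of pharmacy-related total cost of care will be compared between treatment groups using the same approach as for the primary outcome". Logit mixed models then cover "90-day patient-centric, primary care, and avoidable care utilization rates". The sub-analysis sentence comes directly after these: "Sub-analyses of the primary and secondary outcomes using the above methods will be performed on the data stratified by index primary care visit diagnosis".

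Section 1.3 lists the matching secondary objective: "Stratify and report outcomes by index primary care visit diagnoses (substance use disorder, depression/dysthymia, anxiety"). Section 5.1.2, item h, defines the variable: "Primary care visit diagnoses (primary or secondary billed diagnoses"). It gives no hierarchy for patients with more than one of these codes. Eligibility in section 4.3.1 rests on the PHQ-9, not on a billed diagnosis, so a patient can also fall in no stratum.

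The only interaction anywhere in the plan is in the exploratory repeated-measures models: "Fixed effects will be the treatment group indicator, time indicator, and interaction between treatment group and time". Section 6.2 adds "All tests will be two-sided" but states no significance level and no multiplicity rule. Section 6.1 gives no sample size, power, standard deviation, intraclass correlation or stratum size.

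**The concern.** The methods to be reused are arm comparisons, so each stratum receives its own estimate and test for each outcome. Such a set of results cannot answer the question a reader will bring to it, namely whether the programme works differently for patients with different diagnoses. That question is about the difference between effects, and nothing in the plan estimates that difference. A stratum can reach significance while another does not simply because it is larger, less variable or luckier.

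Overlap complicates the reading further. Depression and anxiety can both be billed at one visit, so the same patient can contribute to two or three strata. The stratum results are then correlated, and they are not a partition of the trial.

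A second, smaller issue is when the strata are formed. Practices are randomised before patients accrue, so index-visit billing takes place in a practice already delivering its assigned care. Section 3 lets the provider bring in the programme by live video during the visit. Coding might therefore respond to arm, in which case the arms within a stratum would no longer be fully comparable.

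**Working it through.** The plan states no subgroup figure, so there is nothing to reproduce. The inputs are:

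- Strata: 3 (section 1.3).
- Outcomes per stratum: 5 as section 6.2 is written (total cost, pharmacy cost, three utilization rates). It is 4 if avoidable care is left out, since that rate appears in neither the objectives nor the variable list.
- Significance level: 0.05 two-sided. This is assumed from the 95% confidence intervals in the Protocol Summary.
- Stratum power and correlations: assumed and shown as ranges.

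**Number of tests.** 3 × 5 = 15, or 3 × 4 = 12. Section 6.2 does not say whether the per-protocol analyses are also stratified. If they were, the counts would double to 30 or 24. These are left out of the figures below.

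**Chance of at least one significant stratum result with no true effect.** For k independent tests this is 1 − 0.95^k.

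- k = 15: 1 − 0.95^15 = 53.7%, with 15 × 0.05 = 0.75 false positives expected.
- k = 12: 1 − 0.95^12 = 46.0%.

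Independence is the wrong assumption here: the strata can share patients, and pharmacy claims, where present, are part of total cost. Multivariate-normal simulation (200,000 draws) with correlations of 0 to 0.5 between strata and between outcomes lowers the figures to as little as 41% for 15 tests and 35% for 12. The range is therefore 35-54%.

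**Chance of a mixed pattern for one outcome when the true effect is the same in all three strata.** Mixed means significant in at least one stratum but not in all. For independent strata with equal power p it is 1 − p³ − (1 − p)³. At p = 0.20 this is 1 − 0.008 − 0.512 = 0.48. The correlated columns are simulated.

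| Stratum power | Independent | Correlation 0.3 | Correlation 0.5 |
|---|---|---|---|
| 20% | 48% | 40% | 34% |
| 50% | 75% | 60% | 50% |
| 80% | 48% | 40% | 34% |

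The range is 34-75%. With no true effect at all, the mixed pattern still occurs 14% of the time (independent) or 12% (correlation 0.5).

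**Effect of the fix on the test count.** Testing three flag interactions one by one in five outcomes is 3 × 5 = 15 tests again, with the same 53.7% if independent. One joint test per outcome leaves 4 or 5 tests: 1 − 0.95^4 = 18.5% or 1 − 0.95^5 = 22.6%. Limiting the claim to the primary outcome keeps it at 5%.

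**The case against.** The strongest reply is that the plan promises little here. The other secondary objectives are worded as comparisons, while this one says only that results will be stratified and reported, and section 6.2 calls the work sub-analyses. A reader might infer that the investigators intend to claim different effects by diagnosis; no passage says so. That stands, and labelling the strata descriptive would remove much of the problem. What remains is that the reused methods do produce a test in each stratum, and nothing limits how those results may be read.

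A reader might also infer that coding differences between arms will distort the strata. The documents do not support that. Screening is the same in both arms, and the main outreach starts from a report received the following day, after the index visit. The in-office video request is only a possible route, and nothing in the documents allows its effect to be sized.

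Two further objections are correct. The 53.7% figure is the top of a range, since it takes 15 tests and independence. No particular stratum power has a source in the documents, which is why a wide band is used.

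Finally, replacing index-visit diagnoses with prior ones would change the stated objective and miss newly diagnosed patients. That also stands, so prior diagnoses belong at most in a sensitivity analysis.

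**Conclusion.** The point holds as a weakness of a secondary analysis. The plan refits the primary and secondary outcome models in strata that can overlap and has no arm-by-diagnosis interaction, so it cannot show whether the effect differs by diagnosis. Overlap is not stated in words but follows from counting primary or secondary codes without an exclusivity rule.

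The 35-54% and 34-75% ranges rest on an assumed level of 0.05 per test, assumed correlations of 0 to 0.5 and, for the second range, an assumed equal stratum power of 20-80%. They show that misleading patterns would be common over plausible settings; they are not predictions for this trial.

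Two wider readings are not supported. The sub-analyses do not repeat every test in the plan, because the sub-analysis sentence does not cover the baseline comparisons or the exploratory symptom and health outcomes. Nor does the problem reach the primary intention-to-treat comparison of total cost.

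**What to change.** Amend section 6.2 as follows:

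- For each primary and secondary outcome, fit one intention-to-treat model on all evaluable patients. Keep the practice random effect and add three yes/no flags for the index-visit diagnoses and the interaction of each flag with arm. Separate flags are needed because the diagnoses can overlap and do not form a single three-level factor.
- Use one joint interaction test per outcome. Limit any claim of a differential effect to the primary outcome, or state a multiplicity adjustment.
- Report within-diagnosis estimates with confidence intervals as descriptive, and make no significance claims at stratum level.
- State that a patient may count under more than one diagnosis or under none, and report how many do.
- Compare the frequency of each coded diagnosis between arms. Where earlier diagnoses are available, repeat the analysis with them as a sensitivity analysis only.

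The main change costs a few model terms and some wording. The sensitivity analysis needs a look-back extract that the documents do not describe. The interaction confidence intervals will be wide. The flag interactions, being adjusted for one another, also answer a slightly different question from the simple stratum effects, which is a reason to keep the latter as description.

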There may be cases where patients are eligible to enroll in full case management programs based on their insurance and other criteria –in these situations the VBHI team will coordinate a seamless care transition. For example, if a patient has Medicaid through Cardinal Innovations, a managed care organization providing local behavioral health care, and meets certain criteria, the patient would no longer require services from VBHI team as they would be duplicative.

For the primary and secondary objectives, a patient’s contact with the VBHI program ends after 90 days following the primary care office visit, or if there is a failure to contact, or becomes enrolled with a case-management program which provides behavioral health services, or declines services, or dies. The behavioral health care team will ensure the patient is enrolled in a case management program through contact with staff before ending contact with the patient.

This research project is a parallel group, cluster randomized quality improvement evaluation which seeks to evaluate the total cost of care among patients in the VBHI program for up to 90 days after their primary care visit. The outcomes evaluation of this quality improvement intervention has been designed to integrate into the routine care and minimize frontline staff burden by deploying an evaluation in a real-world setting.

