## 5.2. Virtual Behavioral Health Integration

The flow of patients from initial contact to their follow-up calls is outlined in Appendix 1. In the existing VBHI primary care workflow, all patients are given the PHQ-2 survey. A score  $\geq 2$  triggers the PHQ-9 survey. The following day the behavioral health team receives a patient report. The report

includes patients seen the prior day at intervention sites that had an elevated PHQ-9 score >10 or reported suicide ideation (Question 9 >0). The Monday report includes patients seen Friday-Sunday. Patients associated with Medicare or other value-based insurance plan are identified in the report. The behavioral health care team will reach out to these patients for enrollment utilizing video assessment or telephonic outreach. The patient always has the option not to be followed by the behavioral health care team.

The behavioral health care team will complete the initial behavioral health assessment. The initial health assessment contains information such as preferred communication method, GAD-7, psychiatry provider, collateral resources, recent ED and hospital utilization, substance use disorder, medication barriers, appointment barriers, community resources, and crisis planning.

The frequency of follow-up assessments depends on the clinical presentation and medication recommendation and/or adherence. The assessment includes information such as a suicide ideation safety screening, an appointment reminder, appointment barrier evaluations, medication reconciliation, medication obtainment follow-up, substance use disorder follow-up, supportive listening, psychoeducation, community resource follow-up, and additional crisis planning.

The Columbia-Suicide Severity Rating Scale (C-SSRS) helps identify whether someone is at risk for suicide, and the severity and immediacy of the risk. It also identifies level of support the person needs. The screening tool is administered during each phone contact to measure suicide ideation. Follow-up patients enrolled in the VBHI program will receive follow-up phone calls. The frequency of calls is dependent on the clinical presentation and medication recommendation and/or adherence. A follow-up assessment is completed upon each phone call.

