#### 5.4. Patient Graduation from the VBHI Program

- Reached max benefit as deemed by the behavioral health care team
- Depression remission – PHQ-9 <5 for 2 consecutive months
- Unable to connect: 4 calls attempted over 12 days
- Transition to lower level of care
  - Patients who transition to a primary care clinic not utilizing VBHI services
  - Moved out-of-state
  - Discharged from primary care clinic utilizing VBHI services
- Transition to higher level of care
  - Psychiatry/Treatment Program
- Patient states that they are no longer interested in services but their last PHQ-9 >5
- Declined or no longer interested in services
- Death

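### The supplementary per-protocol analysis restricts mainly the VBHI arm and sets no limit on post-contact covariates, so as written it cannot be read as the effect of participation

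*Combined protocol and SAP*

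**What the plan says.** Section 6.2 puts intention to treat first, by practice assignment, and limits adjustment in that model to data from before follow-up: "Additional baseline covariates will be included in the model" if they are correlated with cost or imbalanced.

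The per-protocol analysis is added to this as an estimate of the effect of participation. Its rules, also in section 6.2, are:
- Analysis set: "The per-protocol analyses will include only subjects who received and adhered to the treatment" assigned to their clinic. Adherence is not defined for either arm.
- Model: "The analyses will be similar to those described above for ITT", with treatment received replacing treatment assigned.
- Adjustment: "the per-protocol analyses will adjust for pre-randomization and post-randomization factors that predict adherence".
- Choice of factors: a logistic regression that "will be performed on the full dataset with adherence (yes/no) as the dependent variable".

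Section 4.4 names intention to treat and per-protocol side by side for the primary outcome, without ranking them.

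The ways out of VBHI are described elsewhere. Section 5.2: "The patient always has the option not to be followed by the behavioral health care team". Section 5.4 lists "Unable to connect: 4 calls attempted over 12 days" in one graduation list with remission, maximum benefit, declining and death. Section 3 ends contact after 90 days "or if there is a failure to contact, or becomes enrolled with a case-management program", on declining, or at death. Section 5.3 describes no behavioural health follow-up in usual care once the patient leaves the practice.

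**The concern.** Two features pull against the stated purpose.

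First, the restriction is lopsided. In the VBHI arm it selects patients who were reached, accepted and stayed. In usual care there is no programme to refuse or leave, so it probably removes few patients. The comparison is then between a selected group and a nearly unselected one. Because the exits in sections 3 and 5.4 are not classified, two analysts could also build different analysis sets from the same data.

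Second, the adjustment has no time limit. Cost is the sum of paid claims in the 90 days after the index visit (section 5.1.1), and that is also when adherence is decided. An acute encounter in that window may be changed by VBHI, may affect whether a patient stays, and is itself part of the cost. If it enters as a covariate, part of the effect is removed.

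At stake is a supplementary result that could be reported as the participation effect when it reflects selection, or that could hide a real effect.

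**Working it through.** The plan gives no adherence rate, cost variance, sample size or power figure, so there is none of its own to reproduce. The only effect size is in section 6.1: $860.16 per member per year, or 10.8%, from a non-virtual programme. This implies a base of 860.16 / 0.108 = about $7,964 per year. Over 90 days that is 7,964 x 90/365 = about $1,964, with a saving of 860.16 x 90/365 = about $212. Every other input below is an assumption.

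**Step 1: which covariates are allowed.** The intention-to-treat model takes baseline covariates. The per-protocol model is similar but adds post-randomization predictors of adherence. No weighting is named and no time limit is given. Practices are randomised before patients accrue (sections 4.1 and 4.2), so index-visit data are also literally post-randomization. The plan's split therefore does not separate safe from unsafe covariates; the split that matters is before or after VBHI contact.

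**Step 2: selection alone, unadjusted.** Suppose VBHI has no effect and all usual-care patients are kept. Let p be VBHI participation and D the cost gap between participants and non-participants, as a percentage of mean cost. Then bias = (1 - p) x D.

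| p | Spurious saving if participants cost 20% less | Gap needed to mimic 10.8% = 10.8 / (1 - p) |
|---|---|---|
| 30% | 14.0% | 15.4% |
| 50% | 10.0% | 21.6% |
| 70% | 6.0% | 36.0% |
| 90% | 2.0% | 108% |

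**Step 3: selection after baseline adjustment, no true effect.** This simulation had log-normal cost (log-SD 1.2), four measured baseline factors in the regression, one unmeasured predictor of adherence (-0.5 log-odds per SD), and adherence of 30%, 50% or 70%. Residual bias was about -2% to -8% of mean cost when the unmeasured factor correlated 0.1 or 0.2 with log cost, and about +2% to +4% when it correlated -0.1. It was within 0.6% of zero when the factor was unrelated to cost. Intention to treat stayed within 0.5% of zero.

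**Step 4: a post-index encounter.** In a second simulation the encounter rate was 12.5% in usual care, VBHI multiplied its odds by 1, 0.92, 0.85 or 0.75, and the encounter lowered the log-odds of staying by 0.4 or 0.8. It cost 4 times the mean of other cost. Adherence was again 30%, 50% or 70%. An unmeasured health factor affected the encounter and cost, but not adherence.

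| True effect | Regression on baseline and encounter | Baseline-only regression |
|---|---|---|
| 0 | within 0.3% of zero | -2.8% to -11.1% |
| -10.8% | -7.8% to -8.4% | -13.1% to -20.5% |
| -10.2% | -5.2% to -5.7% | -12.4% to -19.3% |
| -10.4% | -2.5% to -2.9% | -12.2% to -18.6% |

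Share of the effect removed by regressing on the encounter:
- (10.8 - 8.4)/10.8 to (10.8 - 7.8)/10.8 = 22% to 28%
- (10.2 - 5.7)/10.2 to (10.2 - 5.2)/10.2 = 44% to 49%
- (10.4 - 2.9)/10.4 to (10.4 - 2.5)/10.4 = 72% to 76%

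**Step 5: which weighting works.** A separate simulation of the same kind had about 47% adherence and a true effect of about -10% to -11%.

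| Analysis | Estimate |
|---|---|
| Regression on the encounter | -3.1% to -8.5% |
| Baseline-only regression | -13.1% to -18.4% |
| Weights from one adherence model in the intervention arm | -8.1% to -10.4% |
| Two-step weights: enrolment, then continuation | -9.9% to -11.1% |

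When the weights used encounters that came after the exit, the two-step version gave -7.4% and the single model -4.8%, against a true -11.7%. The order of events therefore matters.

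**The case against.** The strongest reply is that the harmful reading is inferred. The plan says it will adjust, not how, and a separate adherence model is also the first step of weighting. The phrase about post-randomization factors might mean only index-visit data. This stands as a limit on the claim: the text permits regression on later events but does not prescribe it. It is still the natural reading of a model described as similar to the intention-to-treat one, and nothing rules later events out.

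It can also be said that, in Step 4, regressing on the encounter created no false saving and only attenuated a true one, while baseline-only regression did worse under the null. That is correct, and it is why a baseline-only rule must not be adopted alone. Attenuation is not guaranteed either. In a separate check in standardised units, with no true effect and no unmeasured selection, adding a post-index factor moved the estimate from 0.002 to 0.061. With unmeasured selection, the two biases happened to cancel (-0.002).

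The success of weighting in Steps 4 and 5 depends on measured predictors of adherence and on the encounter preceding the exit. Outreach starts the next day and failed contact is declared after 12 days, so much non-enrolment may be settled early. Both points stand and shape the fix.

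The high share of usual-care patients kept is also an inference: no rule or rate is given, and 36 other practices in the system already offer VBHI (section 3).

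Finally, section 6.2 already puts intention to treat first and claims only to help address confounding. That limits the consequence, but section 4.4 does not repeat the ranking.

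**Conclusion.** The point holds for the per-protocol analysis only. As written, it selects mainly within the VBHI arm, leaves adherence undefined, and permits adjustment for events that VBHI may change and that form part of the outcome. The change should be made, but it is not critical, because the analysis is supplementary.

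Size and direction cannot be derived from the documents. The figures above show what is possible under assumed inputs: several percent of mean cost either way from unmeasured selection, and loss of roughly a fifth to three quarters of a true effect from regressing on an encounter. They ignore clustering within the 20 practices. At about 90% participation the selection part is small.

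A reader might infer more than this:
- That the trial's main cost comparison is biased. It is not; the intention-to-treat model uses practice assignment and baseline covariates.
- That the per-protocol result will exaggerate savings. The documents do not fix the direction.
- That weighting would make the result unbiased. It cannot correct for unmeasured predictors of adherence.
- That in-office video assessment changes the billed index diagnoses. Nothing in the documents says so.

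**What to change.** In section 6.2:
- (a) Define adherence in each arm, and state how each exit in sections 3 and 5.4 counts in the analysis, including remission, maximum benefit, transfer and death.
- (b) Limit outcome-model covariates to those recorded at or before the index visit and before any VBHI contact.
- (c) Replace the adherence regression on the pooled dataset, which would largely model arm membership if nearly all usual-care patients count as adherent. Use inverse-probability weights fitted within the intervention arm in two steps: enrolment, from pre-contact factors only; then continuation among enrolled patients, from factors dated before the exit and never from events after it. Do not adopt (b) without (c).
- (d) State that the result supports intention to treat and remains open to bias from unmeasured predictors of adherence, and align section 4.4.

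The cost is SAP wording and modest programming, with dated exits and encounters. Items first collected at VBHI contact, such as GAD-7 or the social questions if asked then, could not be outcome-model covariates or enter the enrolment step. The per-protocol interval widens somewhat: in the weighted runs of the Step 4 simulation, variance inflation in the VBHI arm was 1.01 to 1.12, so up to about 6% on the standard error (square root of 1.12 = 1.058). It would be more if adherence is more predictable.

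A complier average causal effect, with practice assignment as instrument, is an optional sensitivity analysis and not part of this fix. Its interval would be about 1/p times the intention-to-treat interval (2.0 times at 50% enrolment), and it assumes that assignment affects cost only through enrolment.
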